6.6.1. Adverse Events

Adverse events will be reported in accordance with the sponsor reporting standards.

6.6.2. Laboratory Data

Laboratory data will be listed and summarized by treatment in accordance with the sponsor reporting standards. Baseline is defined as the last visit prior to Day 1.

6.6.3. Vital Signs

Absolute values and changes from baseline in supine systolic and diastolic blood pressure, oral temperature, and pulse rate will be summarized by treatment in accordance with the sponsor reporting standards. Tables will be paged by parameter. Baseline is as defined in [Section 3.4](#).

Mean changes from baseline for supine systolic and diastolic blood pressure, oral temperature, and pulse rate for each treatment will be plotted against time post-dose. On each plot there will be 1 line for each treatment. Corresponding individual plots of changes from baseline will also be produced for each treatment.

Maximum absolute values and changes from baseline for vital signs will also be summarized descriptively by treatment, using categories as defined in [Appendix 5](#). Numbers and percentages of subjects meeting the categorical criteria will be provided. All planned and unplanned post-dose timepoints will be counted in these categorical summaries. All values meeting the criteria of potential clinical concern will be listed.

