The study is a phase 2, randomized, dose-finding study of safety, tolerability, pharmacokinetics, and efficacy. Approximately 63 participants will be randomized to one of three doses (1mg/kg once weekly, 2 mg/kg twice-weekly, 1.5 mg/kg once-daily) for 12 months. Participants will be children diagnosed with achondroplasia aged ≥ 3 months to < 11 years; enrollment will progress in an age and dose staggered manner (descending age and ascending dose). Progression to the next enrollment block will be after review of safety and PK data, including review by an external data monitoring committee (eDMC) if safety signals are identified. In order to minimize bias in measurement of the primary efficacy endpoint (height), the anthropometrist will be blinded to dose assignment. There will be no additional blinding.

An interim analysis will be performed when approximately 45 participants (up to 15 participants per dose) aged ≥ 2 to < 11 years have received 6 months of treatment with reciferecept.

All participants who complete the study and in the opinion of the investigator, continue to have a positive risk: benefit profile, will be offered to enroll into an open-label extension (OLE) study. Participants will continue to receive reciferecept at the dose previously received in this phase 2 study or at the therapeutic dose once this is identified.

PK Study Cohort:

At selected sites only, an additional PK cohort has been added to evaluate the PK of two reciferecept formulations (process 1c and process 2). A total of 12 children with achondroplasia aged 2- < 11 years will be enrolled in the PK cohort (6 in each treatment sequence). Each participant will receive 2 treatments (3 mg/kg Phase 2 formulation [process 1c] and 3 mg/kg Phase 3 formulation [process 2]) in a randomized manner according to one of two sequences.

Number of Participants

Approximately 54 participants aged 2-10 inclusive at the time of informed consent will be randomly assigned to study intervention enrolled such that approximately 45 evaluable participants complete the study. In addition, 9 participants aged ≥ 3 months - 2y at the time of informed consent will be enrolled in **CCI** cohort.

PK Study Cohort:

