4. STUDY DESIGN

4.1. Overall Design

This is a phase 2 randomized, 3 arm (3 active doses of Recifercept), parallel group dose- finding study of safety, tolerability, PK and efficacy.

The study will enroll approximately 54 children with achondroplasia aged 2-10 years (inclusive) who will be enrolled and randomized to receive one of three doses of reciferecept (1 mg/kg once-weekly, 2 mg/kg twice-weekly or 1.5 mg/kg once-daily, n=18 per dose) such that approximately 45 participants are evaluable (up to 15 participants per dose). Additionally, **CCI** cohort of approximately 9 children with achondroplasia, ages 3 months to 2 years, will be enrolled later in the study (n=3 per dose). All 63 participants in this part of the study will receive reciferecept for 12 months.

PK Study Cohort:

At selected sites only, an additional PK cohort has been added to evaluate the PK of two reciferecept formulations. A total of 12 children with achondroplasia aged 2- < 11 years will be enrolled in the PK cohort (6 in each treatment sequence). Each participant will receive 2 treatments (3 mg/kg Phase 2 formulation [process 1c] and 3 mg/kg Phase 3 formulation [process 2]) in a randomized manner according to one of two sequences as outlined in [Table 1](#) below. Dose of the cohort could be changed due to emerging safety and efficacy data in the study.

PK samples collected following each dose will be analyzed to evaluate the exposures of two formulations.

Table 1. Treatment Sequence

Sequence	Period 1	Period 2
1 (n = 6)	Phase 2 study (process 1c) Formulation	Phase 3 study (process 2) Formulation
2 (n = 6)	Phase 3 study (process 2) Formulation	Phase 2 study (process 1c) Formulation

All participants who complete the study and in the opinion of the investigator, continue to have a positive risk: benefit profile, will be offered to enroll into an open-label extension (OLE) study. Participants will continue to receive recifercept at the dose previously received in this phase 2 study or at the therapeutic dose once this is identified.

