8.2.4. Electrocardiograms

Standard 12-lead ECGs utilizing limb leads (with a 10 second rhythm strip) should be collected at screening and at Day 4 using an ECG machine that automatically calculates the heart rate and measures PR, QT, and QTc intervals and QRS complex. Alternative lead placement methodology using torso leads (eg, Mason-Likar) is not recommended given the potential risk of discrepancies with ECGs acquired using standard limb lead placement. All scheduled ECGs should be performed after the participant has rested quietly for at least 10 minutes in a supine position (where possible).

ECGs in this study are conducted at screening to document baseline ECG characteristics prior to dosing.

In some cases, it may be appropriate to repeat abnormal ECGs to rule out improper lead placement as contributing to the ECG abnormality. It is important that leads be placed in the same positions each time in order to achieve precise ECG recordings. If a machine-read QTc value is prolonged, as defined above, repeat measurements may not be necessary if a qualified medical provider's interpretation determines that the QTc values are in the acceptable range.

ECG values of potential clinical concern are listed in [Appendix 6](#). However, these should be considered in light of age-specific norms.

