Appendix 5. Categorical Classes for Vital Signs of Clinical Concern

Categories for Vital Signs

Systolic BP (mm Hg)	min. < 90	
Systolic BP (mm Hg) change from baseline	max, decrease \leq 30	max, increase \leq 30
Diastolic BP (mm Hg)	min. < 50	
Diastolic BP (mm Hg) change from baseline	max, decrease \leq 20	max, increase \leq 20
Supine pulse rate (bpm)	min. < 40	max. > 120

PFIZER CONFIDENTIAL
Page 31

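### The absolute vital-sign limits of concern have no age bands and no baseline condition, so the post-dose counts mix pre-existing and age-related values with change on treatment

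*SAP*

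**What the plan says.** SAP 6.6.3 summarises vital signs by treatment "using categories as defined in" Appendix 5. The unit is the child: "Numbers and percentages of subjects meeting the categorical criteria will be provided". The counting window is open: "All planned and unplanned post-dose timepoints will be counted in these categorical summaries". Values of potential concern are also listed.

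Appendix 5 has two kinds of row.
- **Absolute rows:** systolic below 90, diastolic below 50, and pulse below 40 or above 120. None has an age band or refers to the child's baseline.
- **Change rows:** "Systolic BP (mm Hg) change from baseline" and a matching diastolic row. Pulse has none.

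The population is wide in age. Protocol 4.1 states: "The study will enroll approximately 54 children with achondroplasia aged 2-10 years (inclusive"), 18 per dose. It adds a younger cohort of about 9, "ages 3 months to 2 years, will be enrolled later in the study (n=3 per dose"). All three arms are active.

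Two other safety displays are treated differently. SAP 3.5.2 judges laboratory abnormalities with regard to whether the child's baseline was inside or outside the reference range. Protocol 8.2.4 says of ECG values of concern that "these should be considered in light of age-specific norms". The vital-sign rule has neither provision.

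**The concern.** Blood pressure and pulse at rest depend on age in children, so a single cut-off is not equally far from the usual value of an infant and of a ten-year-old. The absolute rows also do not ask whether the child was beyond the limit before the first dose. A child whose ordinary reading lies past a limit enters the post-dose count with no change at all. Taking the worst of many readings adds further children by visit-to-visit variation alone.

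Safety is a primary objective, and change in vital signs is a secondary safety endpoint. With no placebo or untreated arm, nothing in the trial shows what these counts would be off drug. Enrolment runs from older to younger children and from lower to higher dose (Protocol 4.1), and Protocol 6.3.1 states no stratification by age. A difference between dose columns could therefore partly reflect age mix.

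**Working it through.** The plan states no expected rate for these rows, so there is no figure to reproduce.

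**Number of looks.** The main-cohort schedule (Protocol 1.3) gives a completer 9 post-dose vital-sign visits: Days 4, 8, 15, 29, 61 and 91, and Months 6, 9 and 12. In the extracted text the last marks in that row appear shifted by one column; I read them as Month 12 and early termination. Unplanned readings add to the 9.

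**Effect of repeated looks.** This step needs no paediatric norm. If each visit independently meets a limit with probability p, the chance of being counted at least once in K visits is 1 − (1 − p)^K. Setting this to 0.5 gives p = 1 − 0.5^(1/K).
- K = 9: p = 7.4%. K = 8: 8.3%. K = 10: 6.7%.
- With K = 9: p = 2% gives 17%, 5% gives 37%, 10% gives 61%, 20% gives 87%.

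**Effect of norms and within-child correlation.** The documents give no paediatric values, so these are assumptions with a range. I used 100,000 simulated children per scenario, normal readings, one baseline and 9 post-dose visits, within-child correlation 0.3 to 0.7, no drug effect, and the three signs independent of each other. All percentages are of all children and refer to meeting any absolute row.

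| Assumed mean systolic / diastolic / pulse (SD) | At one reading, so also at baseline | Ever post-dose | Ever post-dose, no row met at baseline |
|---|---|---|---|
| 110 / 70 / 80 (9 / 8 / 10) | 2% | 9–14% | 7–13% |
| 105 / 65 / 85 (10 / 8 / 12) | 10% | 32–49% | 24–42% |
| 100 / 60 / 95 (10 / 9 / 13) | 29% | 67–86% | 40–59% |
| 95 / 55 / 105 (10 / 9 / 14) | 58% | 91–99% | 34–41% |
| 90 / 50 / 120 (10 / 9 / 15) | 87% | 99–100% | 12% |

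The first numeric column is the share of children beyond a limit before any dose. The SAP rule does not separate these children from those who cross a limit after dosing.

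**By row.** The SAP tabulates rows, not their union. In the 100/60/95 scenario the ever-flagged rates are 41.5–62.3% for systolic, 37.2–56.3% for diastolic and 10.8–17.5% for pulse.

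**Limits of this check.** The last column drops a child who met any row at baseline. A row-by-row rule would give different figures. Independence between signs is a simplification.

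**The case against.** The strongest reply is that these rows are one descriptive display among several. SAP 6.6.3 also provides change-from-baseline summaries, mean and individual change plots, and a listing of values of concern. No block-progression criterion in Protocol 6.6.1 uses these rows, and clinically significant findings become adverse events on the investigator's judgement. A reader might therefore infer too much in saying that baseline is ignored for vital signs: it is ignored only in the absolute rows. That stands. For pulse, however, the absolute limits are the only categories.

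Age is also partly separated elsewhere. SAP 5.2 presents data by dose group and block, and Protocol 9.4.1 plans separate summaries by dose for children under 2. This stands in part. Blocks are not age bands: the Block B to C review covers both 2–6-year-olds and high-dose 6–10-year-olds. Ages 2 to 10 have no planned age split, and SAP 6.4 plans no subset analyses.

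Protocol 8.2.3 has an abnormal blood pressure repeated after a minute without saying which reading is recorded. If the repeat replaces the first, isolated low readings would be fewer than simulated.

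Two stronger readings are tempting, and the documents support neither.
- *Most untreated, normal children would be flagged.* This rests entirely on norms that the documents lack. The scenarios above run from 9% to 100%, and they describe a union of rows that the SAP does not tabulate.
- *The table cannot show a signal.* Assume mean systolic rising from 94 at age 2 to 106 at age 11, between-child SD 6 and visit-to-visit SD 8. A true 5 mm Hg fall then moves the systolic row from 58% to 79%. The display is blurred, but it still responds.

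**Conclusion.** The point holds as a gap in the safety tabulation, and correcting it is a cheap improvement. The text establishes one set of absolute limits for 3 months to under 11 years, a count over all post-dose readings, no baseline condition on those rows, and no change row for pulse. The 7.4% per-visit figure rests on 9 visits and independent readings. Positive within-child correlation lowers the share ever flagged for a given per-visit rate.

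The actual background rate is unknown. The 9–100% range for any row rests on assumed norms and shows only that the rate is highly sensitive to where a child's usual values lie. What follows is that the counts mix pre-existing and age-related values with post-dose change, with no untreated arm to separate them. How many children this affects, and whether any dose comparison would be distorted, the documents do not show.

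**What to change.** In SAP 6.6.3, count a child as a post-dose case for a category only if that category was not met at baseline, or replace the absolute-row counts with a baseline-to-worst shift table. SAP 3.4 already defines the vital-sign baseline (Day 1, with the latest screening value if Day 1 is missing), so no new data are needed. Present the result by dose within age band: 3 months to under 2, 2 to under 6, and 6 to under 11 years. The shift table is the more informative choice because it keeps every child visible.

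Separately, the sponsor's medical team should reconcile the single set of limits in Appendix 5 with the age range enrolled. No limit value is proposed here.

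The cost is a SAP edit, some table programming and a departure from the sponsor's standard template. Cells will be small: 3 per dose under 2 years, and 18 per dose shared between the two older bands (9 each if the split were even, which is an assumption). The baseline condition removes pre-existing cases but not the effect of repeated looks: 40–59% remain in the 100/60/95 scenario. The counts should still be read as descriptive.

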6.6.4. Electrocardiograms

A single 12-lead ECG will be obtained on all subjects at screening. A listing of clinical ECGs -- comprising QT, heart rate, QTcB, QTcF, PR, RR and QRS – will be presented.

6.6.5. Physical Examination

Physical examination assessments will be listed and summarized by treatment in accordance with the sponsor reporting standards. Baseline is as defined in [Section 3.4](#).

6.6.6. Neurological Examination

Neurological examination will be listed and summarized by treatment. Baseline is as defined in [Section 3.4](#).

7. INTERIM ANALYSES

7.1. Introduction

There will be an interim analysis will be performed to assess efficacy and safety after at least approximately 45 participants (15 per dose), complete their study participation through 50% of the study (completion of 6 months treatment). Interim analysis results may be used for internal business decisions regarding future study planning, though not stopping for futility, stopping for early success nor conducting a sample size re-estimation.

7.2. Interim Analyses and Summaries

Height Growth & Arm span to height/length difference

- Estimand strategy: Hypothetical ([Section 2.1.1](#)).
- Analysis set: FAS ([Section 4](#)).
- Analysis methodology: Change from baseline relative to Merker (2018) will be analyzed using MMRM including data from Months 3 and 6, with gender as a covariate, subject (and/or time) as a random effect and an unstructured covariance matrix ([Section 5.2.1](#)).
- Intercurrent events and missing data: Data after study drug discontinuation and rescue will be excluded; intermediate missing values will not be imputed.
- The sample size, mean, standard deviation, median, minimum, and maximum at the baseline and postbaseline visits for observed standing height (and arm span to standing height difference) and change from baseline will be presented for each treatment arm.

The least-squares (LS) means, the 95% confidence interval for the LS means, the difference between the LS means for each pair of treatment groups, and the corresponding 95% confidence interval will be presented for change from baseline in standing height (and arm span to standing height difference) for all postbaseline visits.

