2.2.1. Clinical Overview

As of September 2021, a total of 32 participants were enrolled from 2 to 10 years old. 14 participants were randomized to 1 mg/kg once weekly (QW) arm and 15 participants were randomized to 2 mg/kg twice weekly (BIW) dosing arm and 3 participants were randomized to 1.5 mg/kg daily (QD). A total of 36 treatment related AEs were reported from 13 out of 32 participants; 3 at low dose, 8 at medium dose and 2 at high dose. The most frequently reported AEs were ISRs such as redness/rash/erythema/pruritis at the injection site. All AEs were mild or moderate in severity and there were no serious adverse events. There were no other clinically significant laboratory abnormalities or physical examination/vital sign changes. Following, administration of study drug, observed serum recifercept concentrations at all three doses were in the range of the predicted exposures in 2 to <10 year old children with achondroplasia using the population PK (PopPK) model.

In the recifercept Phase 1 study (C4181002), healthy participants were administered single (n=30) and multiple (n=24) SC doses of recifercept. In addition, 18 participants received placebo in the study. The dose-range studied in single ascending dose (SAD) part of the study was 0.3 – 20 mg/kg and in the multiple ascending dose (MAD) part was 1 mg/kg and 3 mg/kg twice weekly and 3 and 10 mg/kg once weekly for four weeks. Signs and symptoms of an injection site/infusion site reaction, including erythema, swelling, pain, inflammation, and pruritis, were the most frequently reported adverse events in the SAD and MAD part of

the study. There were no clinically significant changes in laboratory tests, vital signs or ECG. No systemic allergic reactions or serious adverse events occurred during the study.

In the SAD portion of the study, all participants were ADA negative (ADA-) prior to treatment with reciferecept. A confirmed ADA positive (ADA+) response was observed in 8 participants receiving reciferecept and 1 placebo participant at the end of the study (Day 29). In the MAD portion of the study, 2 participants were ADA+ prior to treatment with reciferecept. The majority of the participants who received multiple doses of reciferecept were ADA+ (21/24) and 2 placebo participants during the observation period.

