6.6.1. Rules for Progression to Next Enrollment Block

The eDMC will meet after block A participants have received 4 weeks of study intervention (completed D29) to review safety and PK data. They will make recommendations on dose levels and progression to block B.

Progression to blocks C and D, will occur without eDMC review if NONE of the following criteria are met:

- Serious Adverse Reaction (IMP-related SAR);
- ≥ 2 participants affected by the same moderate/severe study intervention-related AE;
- ≥ 2 participants affected by an AE of hypersensitivity to study intervention;
- ≥ 2 participants with severe ISRs;
- ≥ 2 participants with ISR leading to withdrawal of study intervention.

If any of these criteria are met then the eDMC must be convened to make a decision on progression to the next enrollment block. In addition, no further participants will be enrolled at that dose (or higher) until eDMC recommendation has been issued.

A sentinel approach will be used in recruiting those aged 2- <6 years in block C such that n=2 at high dose will be dosed followed by a 2-week delay before further dosing occurs in that age group.

The dosing schedule may also be adjusted by the eDMC to expand a dosing cohort to further evaluate safety and/or PK findings at a given dose level or to amend the doses to be studied in each enrollment block. The study procedures for these additional participant(s)/cohort(s) will be the same as that described for other study participants/cohorts.

In addition, following evaluation of the overall benefit:risk assessment at the interim analysis, the dose levels may be adjusted. If a new dose level is introduced then this will form a new cohort (minimum n=15) of treatment naïve participants. Previously treated subjects at a discontinued dose will be moved to the next lowest continuing dose.

Any dose modifications will not exceed the current maximum dose (1.5mg/kg once-daily) without submission and approval of a protocol amendment.

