6. ANALYSES AND SUMMARIES

6.1. Primary Endpoint(s)

6.1.1. Increase in height growth above expected in reference population

6.1.1.1. Main Analysis

- Estimand strategy: Hypothetical ([Section 2.1.1](#)).
- Analysis set: FAS ([Section 4](#)).
- Analysis methodology: Change from baseline relative to Merker (2018) will be analyzed using MMRM including data from Months 3, 6, 9, and 12 with gender (and possibly age) as a covariate, subject (and/or time) as a random effect and an unstructured covariance matrix ([Section 5.2.1](#)).
- Intercurrent events and missing data: Data after study drug discontinuation and rescue will be excluded; intermediate missing values will not be imputed.
- The sample size, mean, standard deviation, median, minimum, and maximum at the baseline and postbaseline visits for observed standing height and change from baseline will be presented for each treatment arm.
- The least-squares (LS) means, the 95% confidence interval for the LS means, the difference between the LS means for each pair of treatment groups, and the corresponding 95% confidence interval will be presented for change from baseline in standing height for all postbaseline visits.

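### The interim MMRM stops at Month 6, so it leaves out the Month 9 and possibly Month 12 heights that many low- and medium-dose children are likely to have by the cut

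*SAP*

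**What the plan says.** SAP 7.1 triggers the interim "after at least approximately 45 participants (15 per dose), complete their study participation through 50% of the study", that is, after 6 months of treatment. SAP 7.2 then analyses height growth and the arm span to height difference "using MMRM including data from Months 3 and 6, with gender as a covariate". The final height analysis in SAP 6.1.1.1 is fitted "using MMRM including data from Months 3, 6, 9, and 12".

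The visit limit appears only in the model bullet of SAP 7.2. The descriptive summaries there cover baseline and postbaseline visits without naming Months 3 and 6. The closing sentence promises least-squares means at every visit after baseline, although the model contains only two.

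Protocol 2.2.1 reports that, as of September 2021, "14 participants were randomized to 1 mg/kg once weekly (QW) arm", with 15 on the medium dose and 3 on the daily dose. Protocol 6.6.1 says that, "following evaluation of the overall benefit:risk assessment at the interim analysis, the dose levels may be adjusted".

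**The concern.** Enrolment ascends in dose, so the daily arm fills last and its 15th child sets the date of the cut. Most low- and medium-dose children entered earlier and are likely to be past Month 6 by then. The efficacy hypothesis concerns growth at 12 months (protocol 9.1, SAP 5.1). Later heights bear directly on that question, and on whether early growth is sustained. The interim model omits them when dose levels may be adjusted (protocol 6.6.1), the eDMC reviews efficacy (protocol 4.1), and results may feed future study planning (SAP 7.1).

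**Working it through.** **The plan's own figure.** Protocol 9.2 gives SD 0.15, +50% over reference, 15 per dose and one-sided 0.017, with power over 90%. Treat one dose as a one-sample comparison with a fixed reference ratio of 1. Then SE = 0.15/√15 = 0.039, 0.5/0.039 = 12.9, and power exceeds 0.9999. The stated figure holds as a lower bound.

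**Who has later heights at the cut?** Inputs:
- Low and medium dose: 14 + 15 = 29 of the 30 children needed were randomized by September 2021.
- Daily dose: 15 − 3 = 12 still needed, on the SAP trigger of 15 per dose.
- Visit days from the protocol schedule: Month 6 = 183, Month 9 = 273, Month 12 = 365.

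Let the 15th daily-dose child enter d days after the September 2021 count. A low- or medium-dose child who entered e days before the count then has d + 183 + e days of follow-up at the cut. Entry dates are not given, so assume uniform low- and medium-dose entry over the previous 150 to 300 days.

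| d (days) | Basis | Month 9 or later | Month 12 |
|---|---|---|---|
| 14 | two-week sentinel delay only (protocol 6.6.1) | 49–75% | 0–44% |
| 43 | 14 + 29, sentinel delay plus a Day 29 review | 69–84% | 7–54% |
| 90 | slower entry | 100% | 39–69% |
| 174 | 30 Sep 2021 to 23 Mar 2022 (protocol amendment 3, dated in SAP section 1) | 100% | 95–97% |

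The Month 12 column counts children who have reached Day 365. At d = 174, even a child who entered on the count date has 174 + 183 = 357 days, inside the SAP Month 12 window (Days 346 to 366, Appendix 2.2's companion table in Appendix 2.1). All values of d are assumptions.

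**Precision versus the reference.** Take 0.15 as the 12-month SD of the growth ratio. Let f be the share of that variance due to true differences between children. The rest is measurement error, whose SD on the ratio scale falls as 1/t (t in years):

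SD(t) = 0.15 × √[f + (1 − f)/t²], and SE = SD(t)/√15.

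| f | SD Month 6 | SE Month 6 | SE Month 12 |
|---|---|---|---|
| 0 (all measurement error) | 0.300 | 0.077 | 0.039 |
| 0.5 | 0.237 | 0.061 | 0.039 |
| 1 (all between-child) | 0.150 | 0.039 | 0.039 |

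The Month 12 SE is therefore between half the Month 6 SE and equal to it. The documents do not give f.

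**Fewer children at Month 12.** With 8 observed, and before any borrowing from earlier visits, SE = 0.15/√8 = 0.053; with 5 it is 0.15/√5 = 0.067. The Month 12 count that only matches Month 6 with n = 15 is 15/[f + 4(1 − f)]: 3.75 at f = 0, 6 at f = 0.5 and 15 at f = 1.

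**What does not improve.** With a separate mean for each dose and visit, complete Month 6 data and covariates ignored, the Month 6 variance is the same with two or four visits (0.006 at f = 0, 0.00375 at f = 0.5). The daily-versus-medium SE at Month 6 stays at √2 times the arm SE: 0.110, 0.087 and 0.055 for f = 0, 0.5 and 1.

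**Effect on power.** In the worst case for Month 6 (SD 0.30), power for +50% still exceeds 0.999. For +25%, 0.25/0.077 − 2.12 ≈ 1.11, so power is 0.87, against above 0.99 at Month 12 with 15 observed.

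**The case against.** Month 6 is the deliberate interim time point: protocol 1.1, 4.1 and 9.5 and SAP 7.1 all define the interim by 6 months of treatment. A common time point keeps the three doses comparable. This stands, and Month 6 should remain the main interim comparison.

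A reader might infer that the later heights are discarded. They are not: the final MMRM uses them, and the interim descriptive summaries are not limited to Months 3 and 6.

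A reader might also infer that all 29 children are well past Month 6 at the cut, or that the interim was still to come in August 2022 because SAP version 2 uses the future tense. Neither follows. No enrolment dates or rates are given, a child who entered in late September 2021 is only at Month 6 by the end of March 2022, and wording in a SAP does not date the interim. The protocol also says up to 15 per dose, so 12 further daily-dose children is the SAP reading rather than a certainty.

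SAP 7.1 rules out stopping for futility or early success and sample size re-estimation. Protocol 6.6.1 ties dose changes to overall benefit and risk, and protocol 9.5 leaves decision criteria to a charter. The later heights would be one input among several.

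Finally, added visits could do harm. The Appendix 4 code has no dose-by-month term, so with unequal follow-up it would mix visits across doses. The early subset may also be older, since Block A was aged 6 to 10. The interaction that SAP 5.2.1 already requires deals with the mixing of visits; a supportive label and reported counts keep the rest in proportion.

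**Conclusion.** The point holds as a worthwhile improvement, not as a flaw that invalidates the interim. The interim model is limited to Months 3 and 6, and staggered enrolment makes Month 9 heights likely for many low- and medium-dose children: about half to all of them across the scenarios above, with Month 12 anywhere from none to nearly all. The gain is confined to those two doses versus the reference. It runs from none to a halved standard error with 15 observed, and is smaller with fewer.

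A single percentage gain in precision is not supportable. It would need an assumed measurement error and full numbers at the later visits, and it compares growth at different time points. For the planned +50% effect, Month 6 alone gives ample power. What the later visits mainly add is evidence nearer the 12-month question. The conclusion rests on 0.15 being the 12-month SD and on the assumed entry patterns.

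**What to change.** In SAP 7.2:
- Keep Month 6 as the common interim comparison for all doses.
- Add a supportive MMRM with every scheduled height available at the cut and the dose-by-visit term required by SAP 5.2.1. Correct the Appendix 4 code, which omits that term.
- Report Months 9 and 12 versus the reference, with the number observed, for doses that meet a minimum number set in advance. Label these results supportive, with no success claim.
- Make the sentence on least-squares means name the visits that each model contains.

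The cost is a few sentences and a code correction. The downsides are small: later visits will be sparse in the daily arm, the early subset may be older, and Month 12 will be seen early for two doses.
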